1.1 Overview of the clinical trial

	Randomised controlled multicentre study of albumin	
Title of the trial	replacement therapy in septic shock	
Trial Acronym	ARISS-Study	
Sponsor according to AMG	Friedrich Schiller University Jena	
Sponsor's legal representative (SpB) and principal investigator (LKP)	[name]. [name] Universitätsklinikum Jena Klinik für Anästhesiologie und Intensivmedizin [name] [contact] [contact] E-Mail: [contact]	
EudraCT Number	2018-001874-89	
Study population	Female and male patients ≥ 18 years treated in the intensive care unit (ICU) within 24 hours of septic shock diagnosis	
Study phase	III b	
Trial design	Prospective, multicentre, randomised, controlled, parallel- grouped, open-label, interventional clinical trial according to the German Medicinal Products Act	
Primary target: To investigate whether albumin administration and maintenance of serum albumin concentrations of a 30 g/l in the ICU for up to 28 days after the onset of shock, will reduce total 90-day mortality compared volume replacement therapy without albumin Secondary targets: - To investigate whether albumin administration at maintenance of serum albumin concentrations of 30 g/l in the ICU for up to 28 days after the onset septic shock would influence ICU, hospital, 28-a day mortality rates, rates of organ dysfunction/far assessed by the SOFA score, ICU/hospital length stay, ventilator and vasopressor-free days. - Cost-benefit analysis of volume replacement the		
Primary outcome (primary	from ICU admission until maximum day 28 Primary outcome: 90-day all-cause mortality	
end-point)		
Secondary outcome	Secondary outcomes:	
(secondary end-point)	 - 28- and 60-day mortality, mortality rates in the ICU and during hospitalization, organ dysfunction/failure as assessed by the SOFA score, ICU and hospital length of stay, ventilator and vasopressor free days. 	

ARISS
EudraCT-Nr.: 2018-001874-89
ZKSJ0112_ARISS
UNIVERSITATS
KLINIKUM
Jena

Sample size	 Cost-benefit parameters of volume replacement therapy (albumin, other colloids and crystalloids) Total amount of fluid of fluid administration and total fluid balance in the ICU. Safety related endpoints: Onset of AEs and SAEs, in particular anaphylactic shock, hypervolaemia, pulmonary oedema and sepsis-related clinical events Assuming a 90-day mortality of 50% in the control group without albumin and 42% in the albumin group, 1412 patients need to be evaluated (power: 80%, Chi²Test alpha

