10.3 Audits and inspections

Within the scope of quality assurance, the SpB can have an independent audit conducted at any time in the participating institutions. In this case, the investigator or the participating institution will grant the auditor access to all documents necessary for the audit.

Inspections as part of the monitoring of ongoing or already completed clinical trials are carried out by the competent authority in accordance with § 64 (1) of the AMG (28). The inspection conducted by the competent authority shall be carried out in accordance with a written procedure and a pre-determined plan.

The SpB and all participating trial centres are committed to supporting inspections by competent authorities and, in this regard, to grant authorised persons access to the original data and documents.

Statistical methods and determination of sample 11. size

Sample size

The 90-day mortality in the control arm is estimated to be about 50% (taking into account the possible use of albumin in the control group) (4, 7, own pilot study).

For the sample size estimation, a 15% reduction in 90-day mortality is assumed, i.e., an absolute reduction of 7.5 percentage points to 42.5% (relative risk 1.18). This limit was chosen because the relatively costly albumin therapy can only be justified if there is a sufficiently clear treatment effect. This assumed effect size has the potential to affect current standard of care and international treatment guidelines and lies between the observed reduction in 90-day mortality in patients with septic shock (13%) and the assumed effect size in the ALBIOS study (23). Following the recommendation of the reviewers of the DFG application of the ARISS study, the sample size was estimated taking into account a centre variability (probably about 50 centres) in mortality of patients in the control arm of the study between 40% and 60% and a risk reduction between 12% and 18% (coincidentally uniform).

A Mantel-Haenszel Chi² test at a two-tailed significance level of 0.05 with a power of 80% requires 1412 patients to be analysed, 706 per arm, to demonstrate such an effect.

This case number estimate can be considered conservative for the planned analysis (nonlinear mixed model taking into account random centre effects).

The case number estimation was performed using SAS 9.4 (SAS Institute Inc., Cary, NC, USA).

Dropout Rate:

Approximately 15%, through

- "loss to follow up" until day 90

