11.2 Randomisation

Randomisation will be stratified according to:

- Serum lactate levels within 24 h before inclusion in the trial: ≤ 8 mmol/l vs. > 8 mmol/l and
- centre

in the treatment groups

- albumin group
- control group without albumin

Albumin administration will be adjusted after the starting dose according to serum albumin concentrations. Therefore, blinding will not be possible.

Group assignment will be determined using a validated electronic tool (PaRANDies) after inclusion of the patient. Randomisation will be based on a randomisation list created in advance with nQuery Advisor 7.0.

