- Total amount of fluid administration in the ICU (individual average amount of fluids given enterally or parentrally, including volume therapy) and total fluid balance in the ICU (individual average difference between daily fluid administration urinary output and other fluid loss): descriptive statistics, especially quartiles.

All secondary endpoints, unless included in the primary analysis model, will be exploratively compared using appropriate parametric and nonparametric tests between treatment groups.

Health economics:

In the context of the ARISS study, a health economic cost-benefit analysis of volume replacement therapy of the ICU stay will be carried out up to a maximum of day 28. The direct costs of colloid, crystalloid and albumin administration will be recorded and the length of stay (first hospitalisation and stay since study participation) evaluated economically to assess whether albumin administration has an effect on hospital costs or not. At the patient level, DEALE (declining exponential approximation of life expectancy) (27) will be applied to calculate patient-specific life expectancy based on mortality rates in the general population and in the disease-specific population. The subsequent cost-effectiveness analysis will yield the cost per year of life for albumin administration. The robustness of the analysis will be checked with one-way and multi-way analyses as well as probabilistic sensitivity analysis.

Analysis of safety parameters:

Frequencies of AEs and SAEs will be analysed using frequency tables. In addition, frequencies of selected AEs (sepsis-related clinical events) will be analysed.

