6.6 Primary Analysis

The primary efficacy variable 90 day mortality will be analyzed with a Generalized mixed model with fixed effects SAPS II score, baseline lactate, baseline-albumin-serum value, type of admission (surgical/non-surgical) and treatment group and random effect center; descriptive statistics will be presented. The primary analysis will take place in FAS according to ITT-principle; an additional sensitivity analysis in PPS will be performed. In addition, descriptive analysis of 90-day mortality in subgroups with respect to baseline-lactate, baseline albumin, baseline SOFA, SAPS II und APACHE II will be performed.

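### No covariates or strata are named for the secondary mortality comparisons, although 90-day mortality in the same patients gets a covariate-adjusted mixed model

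*Protocol*

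**What the plan says.** - **Randomisation.** Protocol 11.2 stratifies by centre and by lactate, cut at 8 mmol/l ("Serum lactate levels within 24 h before inclusion in the trial").
- **Primary endpoint.** Protocol 11.3.2 analyses 90-day mortality with a generalised mixed model: random effects for centre and patient in centre; fixed effects for SAPS II, SOFA, baseline serum albumin and treatment. SAP 6.6 specifies a "Generalized mixed model with fixed effects SAPS II score, baseline lactate, baseline-albumin-serum value, type of admission" and treatment, with a random centre effect, and adds descriptive statistics.
- **Secondary endpoints, protocol.** Section 11.3.2 lists descriptive statistics and Kaplan-Meier estimates for 28-day, 60-day, ICU and hospital mortality. It then says that all secondary endpoints outside the primary model "will be exploratively compared using appropriate parametric and nonparametric tests between treatment groups". No test, covariate, stratum or centre effect is named.
- **Secondary endpoints, elsewhere.** The synopsis (1.1) and SAP 6.7 give descriptive analysis only, with Kaplan-Meier for overall mortality in the SAP. SAP 6.11, on deviations from the protocol, does not mention that the between-group tests have gone.

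**The concern.** Mortality at 28, 60 and 90 days forms a nested set of outcomes in the same patients, and readers will set the three side by side to judge whether an effect is early, late or sustained. If day 90 comes from a covariate-adjusted model and the others from crude comparisons, two things differ besides the time point.

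First, chance imbalance in severity stays in the crude results and is largely removed from the adjusted one. Second, the model gives an odds ratio conditional on covariates and centre, which differs from a crude odds ratio even with perfect balance.

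The crude comparisons also leave unused prognostic data that the trial collects anyway. At stake are the precision and comparability of exploratory results. The primary conclusion is not affected.

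**Working it through.** **The plan's own figure.** Protocol section 11 (Sample size) states: "A Mantel-Haenszel Chi² test at a two-tailed significance level of 0.05 with a power of 80% requires 1412 patients to be analysed", for "an absolute reduction of 7.5 percentage points to 42.5"% from a control rate of 50%.
- Per arm: n = [1.96·√(2·0.4625·0.5375) + 0.842·√(0.5·0.5 + 0.425·0.575)]² / 0.075² = 693. The total is 1386, or 1438 with continuity correction; 1412 lies between. Power at 706 per arm is 80.7%.
- Dropout: 1412/0.85 = 1661.2, so 1662, as stated.
- The synopsis rates of 50% and 42% would need only 1218 to 1266, so 42.5% is used below.

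**Assumptions.** The documents give no mortality rates for the secondary endpoints and no prognostic strength for the covariates. I use 50% mortality, 706 per arm, and one normal prognostic score with SD s on the logit scale, for s = 0.5, 1.0 and 1.5 (AUC about 0.63, 0.74 and 0.81).

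**Gain from covariates.** With p = 1/(1+e^(−sZ)) and Z standard normal, the share of outcome variance explained is R² = Var(p)/0.25. The equivalent sample gain is 1/(1−R²) − 1.
- s = 0.5: 0.0140/0.25 = 5.6%; gain 6%.
- s = 1.0: 0.0434/0.25 = 17.4%; gain 21%.
- s = 1.5: 0.0733/0.25 = 29.3%; gain 41%.

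**Gain from centre.** Protocol section 11 allows control mortality to vary uniformly between 40% and 60% across about 50 centres. The share is (0.2²/12)/0.25 = 1.3%. In 4000 simulated trials on the protocol's centre assumptions, power was 82.1% with a centre-stratified Mantel-Haenszel test and 81.7% with a plain chi-square. The share due to lactate cannot be computed, because the documents give no lactate-mortality association.

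**Chance imbalance.** The 95% range of the shift in a crude mortality difference is 1.96·s·√(2/706)·0.25·(1−R²): ±1.2, ±2.2 and ±2.8 points for the three values of s. The crude 95% half-width is 1.96·√(2·0.25/706) = 5.2 points, which already contains this shift. Removing the explained variance (multiply by √(1−R²)) gives about 5.1, 4.7 and 4.4 points.

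**Scale.** For 50% against 42.5% the crude odds ratio is 0.425/0.575 = 0.74. Solving for the conditional effect that gives the same two rates yields about 0.73, 0.69 and 0.65 for s = 0.5, 1.0 and 1.5. The same effect therefore looks larger in the adjusted model, with no imbalance at all.

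**Simulation** (1500 trials per setting, N = 1412, 50% against 42.5%, AUC 0.66 to 0.82):
- Crude power was 82% to 83%. Adjusted power was 85%, 88%, 90% and 94% at AUC 0.66, 0.72, 0.77 and 0.82.
- On the same data the two methods fell on opposite sides of p = 0.05 in 6% to 14% of trials with the effect present, and in 3% to 5% under the null.
- Crude false-positive rates were 4% to 5%, so the crude test is valid.
- With no prognostic value the power difference vanished.
- One covariate stood for the whole set, the adjusted model had no centre term, and Monte Carlo error is about 1 point.

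**The case against.** A reader might infer that the protocol prescribes plain tests that ignore the strata. It does not: the tests are only called appropriate, and section 11.3.3 leaves analysis details to the SAP. A stratified or model-based test is not excluded, although nothing points to one.

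A reader might also infer that leaving out the strata is itself costly, or peculiar to the secondary endpoints. Centre is worth about 1%, and the protocol's own primary model omits lactate; only the SAP model includes it.

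A third tempting inference is that an early or late effect would be an artefact of method. SAP 6.6 also presents descriptive 90-day results, and SAP 6.7 describes overall mortality by Kaplan-Meier, so a like-for-like crude reading exists. Chance imbalance is not extra bias either, since it lies within the crude interval.

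Finally, the comparisons are exploratory, and under the SAP and synopsis no secondary test would be run at all.

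All of this stands and keeps the point minor. What remains is that neither document gives the secondary mortality endpoints an estimate comparable with the adjusted 90-day result. Purely descriptive output does not supply one.

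**Conclusion.** The point holds as an inexpensive improvement. No secondary comparison has named covariates or strata in either document. On the natural reading, 28-day, 60-day, ICU and hospital mortality are compared crudely beside an adjusted 90-day estimate. Such comparisons are valid and slightly conservative, but less precise and on a different scale.

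Adjustment is worth about 6% to 41% in equivalent sample size, nearly all of it from severity. That range rests on an assumed prognostic SD of 0.5 to 1.5 and on 50% mortality standing in for secondary rates that the documents do not give. The documents do not support a claim that the planned comparisons are biased or invalid, or that the strata drive the loss. Severity: minor.

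**What to change.** In SAP 6.7, with matching text in protocol 11.3.2:
- Analyse 28-day, 60-day, ICU and hospital mortality with the SAP 6.6 model (random centre; SAPS II, baseline lactate, baseline albumin, type of admission, treatment).
- Report each treatment effect with a 95% confidence interval, beside the crude rates by arm for all these endpoints and for day 90.
- Keep these analyses labelled exploratory.

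Do not prescribe one adjusted method for every other secondary endpoint. A stratified rank test or a linear model does not suit length of stay, for example, which the protocol plans as Kaplan-Meier with censoring at drop-out and death.

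The cost is a few sentences and reuse of the primary model code; no new data are needed. There are two small downsides. SAP 5.1 does not replace missing baseline values, so patients lacking a covariate drop out of the model; whatever handling the primary analysis adopts should apply here too. The odds ratio is also conditional, which is why the crude rates should stay beside it.

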11.3.3 Subgroup analyses

The primary endpoint and selected secondary endpoints (SOFA, organ failure defined as SOFA organ failure score ≥ 2) will be described for the following subgroups:

Baseline lactate ≤ 8 mmol/L versus> 8 mmol/L

SOFA total and subscores, SAPS II, APACHE II: by baseline quartiles

Details of the statistical analyses will be described in the Statistical Analysis Plan.

11.3.4 Interim analysis

Not planned.

Zentrum für Klinische Studien

11.4 Presentation of results

The final statistical report will be based on the specifications and checklist of the CONSORT statement on the publication of randomised controlled trials in parallel group design (33) and on regulatory requirements.

12. Regulatory and administrative aspects

12.1 Regulations

The clinical trial will be conducted according to the current protocol, in agreement with the current versions of the German Law on Marketing Authorisation for Medicinal Products (AMG) (28), the ordinance on the Application of Good Clinical Practice in Conducting Clinical Trials with Medicinal Products (GCP-V) (31), the principles published in the ICH GCP Guideline (29), and the ethical principles set out in the Helsinki Declaration in 2008 for clinical trials as a recognised ethical basis (34).

12.2 Ethic committees

According to § 40 AMG (28), a clinical trial on a medicinal product in humans may only be started if the competent Ethics Commission (EC) has approved it in accordance with § 42 (1). For multicentre clinical trials that are carried out within the scope of the AMG in more than one trial centre, each further EC (involved EC) will receive a copy of the application and the documents from the SpB at the same time, according to state law for the respective investigator. Each investigator will receive from the applicant a copy of the approval of the IC for the ISF.

12.3 Competent authorities

12.3.1 Federal authority

For this clinical trial under the AMG, the Federal Institute for Vaccines and Biomedical Drugs (Paul-Ehrlich-Institut (PEI) in Langen) is the competent higher federal authority (BOB). According to § 40 AMG (28), the clinical testing of a medicinal product in humans may only be started if the competent higher federal authority has approved it in accordance with § 42

Each investigator will receive from the applicant a copy of the authorization for the ISF.

12.3.2 State authorities

Pursuant to § 67 AMG (28), each registered investigator/deputy has a general obligation to notify the competent authority. Pursuant to Section 12 GCP-V (31), the investigator may entrust the sponsor with the execution of the notification to the competent authority and must document this.

In each case, the government authorities or the competent authorities in the countries in which a trial centre is located are responsible for the clinical trial. When the sponsorship is taken over by the Friedrich Schiller University Jena or the Jena trial Centre, notification will be made to the Thüringer Landesamt für Verbraucherschutz (TLV) in Bad Langensalza. The respective state report must be filed in the respective trial centre folder.

Subsequent changes in the trial protocol - amendments

According to § 10 (1) GCP-V (31), changes in the trial protocol requiring approval are to be applied for by the SpB and only after approval by the responsible EC, insofar as they relate to the information and documents pursuant to § 7 (2), (3) or (3a) and if they have been approved by the responsible BOB, insofar as they relate to the information and documents pursuant to § 7 (2) or (4). This excludes amendments that are necessary in order to avert immediate danger to the concerned persons (§ 11 GCP-V, (31)), which must be implemented immediately. The SpB will immediately inform the responsible BOB and the responsible EC about these new circumstances. A favourable evaluation should be obtained from the responsible EC and approval should be requested from the responsible BOB. The EudraCT-Nr.: 2018-001874-89 ZKSJ0112 ARISS

application must be reasoned. Even changes that are only subject to approval by the responsible EC are to be reported to the responsible BOB. To ensure largely comparable conditions in all trial centres and in the interest of a flawless data evaluation, there is no intention to perform any amendment or changes to the trial conditions agreed upon in the trial protocol (i.e., study design, course of study or evaluation procedure).

12.5 Registration

Registration of the clinical trial will be done before randomisation of the first patient in the WHO-recognised German Register of Clinical Trials (DRKS, www.drks.de). In addition, the clinical trial will be registered at clinicaltrials.gov. The registry entries will be maintained continuously.

12.6 Insurance

According to § 40 AMG (29), insurance must be taken out by the SpB for all patients participating in the trial.

Subject insurance will be concluded for all patients included according to § 40 AMG in the context of the proband year contract of the hospital of Friedrich-Schiller-University Jena with the HDI Gerling Industrie Versicherung AG, 30659 Hannover. The seat, policy number, telephone number and fax number of the insurance company will be included in the patient information form. Travel accident insurance will not be taken out. Patients will be informed about their rights and obligations in connection with the insurance. Each participant in the clinical trial will receive the conditions of insurance in writing.

12.7 Funding

The German Research Foundation (DFG) will fund the clinical trial within the framework of the program "clinical studies", grant number DFG SA 2167 / 3-1, project number 328809707. The Department of Anaesthesiology and Intensive Therapy of the University Hospital, Jena will take over the financing of the remaining duration of the clinical trial after the DFG funding period has expired.

The trial drug for treatment of the albumin group will be provided free of charge by GRIFOLS SA ([name]).

Reports of the study results

All information concerning this clinical trial must be treated confidentially. According to AMG § 42 b (29), the SPB is required to publish the results of clinical trials within certain deadlines and in compliance with certain requirements.

The SpB is responsible for the preparation of the final report.

Appendix 14.

14.1 SOFA Score

Organ dysfunction is defined according to the SOFA score variables. The worst value of the parameter each day will be used to calculate the score. The parameters of the SOFA score are determined until day 28 exclusively in the intensive care unit and are calculated from the sum of the evaluation points of the individual organ systems listed below. The parameters for calculating the SOFA subscore are also part of the CRF. The score points of each organ system range from 0 to 4. The SOFA score is calculated in the data management center (ZKS Jena). The subscores of the SOFA score are determined as follows:

Cardiovascular System

Mean arterial pressure (MAP) and the need for catecholamine determine the assigned points. The lowest MAP value of the past 24 hours is part of the CRF. The highest catecholamine dosage> 1 h of the past 24 hours is part of the individual variables in the CRF.

Score	Cardiovascular status				
0	MAP ≥ 70 and no vasopressors				
1	MAP < 70 and no vasopressors				
2	Dopamine <5 μg/kg/min oder Dobutamine (and dose)				
3	Dopamine >5 – <15 μg/kg/min or (nor)adrenalin <0.1 μg/kg/min				
4	Dopamine>15 μg/kg/min or (nor)adrenalin >0.1 μg/kg/min				

Pulmonary system

The PaO₂/FiO₂ ratio determines this sub-score. If the blood gas analysis is not available for the day or the patient is no longer intubated, but relies on oxygen therapy, conversion tables will be used.

Score	PaO ₂ /FiO ₂
0	> 400 mmHg (> 53.2 kPa)
1	301–400 mmHg (39.9–53.1 kPa)
2	201–300 mmHg (26.6–39.8 kPa)
3	101–200 mmHg (13.3–26.5 kPa)
4	< 100 mmHg (< 13.3 kPa)

Coagulation system:

The platelet count determines this sub-score. The lowest platelet count of the past 24 hours is part of the CRF variables.

Score	Platelet count
0	$>150 \times 10^{3} / \text{mm}^{3}$
1	100-149 ×10 ³ /mm ³
2	50–99 ×10 ³ /mm ³
3	20–49 ×10 ³ /mm ³
4	$<20 \times 10^{3} / \text{mm}^{3}$

Serum creatinine and urinary output determine this sub-score. The worst value is part of the CRF variables.

Zentrum für Klinische Studien

Score	Serum creatinine and urinary output			
0	<1.2 mg/dl (<110 µmol/l)			
1	1.2–1.9 mg/dl (110 –170 µmol/l)			
2	2.0-3.4 mg/dl (171- 299 µmol/l)			
3	3.5–4.9 mg/dl (300–440 µmol/l) or urinary output <500 ml/24h			
4	≥5,0 mg/dl (≥ 441 µmol/l) or urinary output <200 ml/24h			

Hepatic system:

Total bilirubin determines this value. The worst value is part of the CRF variables.

Score	Total bilirubin
0	<1.2 mg/dl (< 20 µmol/l)
1	1.2–1.9 mg/dl (20–32 µmol/l)
2	2.0–5.9 mg/dl (33–101 μmol/l)
3	6.0–11.9 mg/dl (102–204 μmol/l)
4	≥12 mg/dl (≥205 µmol/l)

Central nervous system (CNS):

The CNS is assessed by the Glasgow Coma Scale (GCS). If the patient is sedated, the assessment of conscious level is based on the observer's assumption that the patient is not sedated. In addition to this esteemed GCS, the actual GCS should also be documented. The worst estimated and worst actual GCS is part of the CRF variables.

Score	Glasgow Coma Scale
0	15
1	13–14
2	10–12
3	6–9
4	≤ 5

Glasgow Coma Scale

The Glasgow Coma Scale is a neurological assessment scoring system composed of three individual assessments, which are summed up below.

	Score		Score		Score
Eye openning		Best motoric response		Beste verbal	
Spontaneous	4	Obey commands	6	Response	
On demand	3	Painful stimulation		Response to verbal	
Painful stimulation	2	localisation	5	contact	
None	1	flexion	4	oriented	5
		Abnormal flexion	3	confused	4
		Extention (decerebrate)	2	Words	3
		None	1	Sounds	2
				None	1

Refernce: Vincent JL, Moreno R, Takala J, et al. The SOFA (Sepsis-related Organ Failure Assessment) score to describe organ dysfunction/failure. Intensive Care Med 1996;22(7):707–710.

Zentrum für Klinische Studien

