6.7 Permitted concomitant medication, concomitant therapies

There are no restrictions to concomitant medication and therapies during the trial. Concomitant medication and therapies must be documented.

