7.5 Trial visits on trial days 1 to 28 after randomisation

These visits should only be performed if the patient is still being treated in the ICU.

- Blood sampling to determine the serum albumin concentration, including recording the time of blood sampling
- Blood samples for serum albumin concentration determination may be performed as part of the routine blood sampling procedure at the respective trial centre, provided that they are taken between 4:00 and 9:00 in the morning.
- Collection of data on infection, microbiology and anti-infective therapy
- Recording of the raw data for calculation of the SOFA score on the respective study day from the routine laboratory results (not for trial purposes); the "worst" daily value should be recorded
- Recording of concomitant medication with catecholamines and inotropes, diuretics, fluid therapy (including transfusion therapy, adjunctive sepsis therapy) on the respective trial day
- Recording of intensive care interventions (ITN, CIC, AC, RRT, mechanical ventilation, ECMO, haemodynamic monitoring) on the respective trial day
- Recording the amount of enteral and parentral fluid adminstration on the trial day
- Collection of routine laboratory data (not trial-related), taken between 4:00 9:00 in the morning: haemoglobin, creatinine, bilirubin, C-reactive protein, procalcitonin, leucocytes, platelets, lactate, arterial blood gas analysis (PaCO2, PaO2, FiO2, SO2, pH, ScO2)
- Recording of clinical parameters (body temperature, respiratory frequency and haemodynamic parameters), 24 h urinary output, other fluid loss on the trial day
- Capturing of AEs/SAEs and sepsis-related clinical events (continuous)
- Recording of vital status (live / dead)
- Albumin group: administration of the trial drug according to serum albumin concentration, dose adjustment according to the given scheme
- Data collection regarding administration of the trial drug (continuous), including information on the administered dose, interruption or discontinuation of the dose if necessary Note: After administration of the trial drug on day 28, no further doses are given.

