11.3.2 Data analysis

General methodology:

All collected data will be analysed using descriptive methods in the two treatment groups. This includes at least:

- the number of values collected and missing, mean, standard deviation, minimum, quartiles including median and maximum for continuous variables and
- frequency analyses for ordinal and categorical data.
- At baseline, the last available value will be used no later than the period up to 2 hours after randomisation, but before the start of albumin administration.

Baseline and population characteristics, demographics:

Demographic variables, SAPS II, APACHE II: descriptive analysis

Primary analysis:

The primary endpoint, "90-day mortality" (M90), will be calculated using a generalised mixed model with the random effects "centre" and "patient in centre" and the fixed effects SAPS II, SOFA and "baseline serum albumin value" as well as " treatment group "to the significance level Alpha = 0.05 analysed bilaterally.

The null hypothesis, M90 (control group) = M90 (albumin infusion), will be tested against the alternative M90 (control group) \neq M90 (albumin infusion).

The primary analysis will be conducted in the ITT population.

Additional sensitivity analyses:

- Analysis in the PP population
- If more than 10% of M90 data are missing: multiple imputation analysis based on observed mortality rates, SOFA scores, ICU stay, and hospital stay.

Secondary endpoints:

- 28-day, 60-day, intensive care and hospital mortality: descriptive statistics, Kaplan-Meier estimates on mortality.
- Organ failure defined as increase in the daily recorded SOFA (day 1 to 28) from a value <2 to a value ≥ 2, individual number of organ failures in the period from day 1 to day 28: descriptive statistics, Kaplan-Meier estimates for the date of the individual first organ failure
- SOFA score: descriptive statistics
- Length of stay (after randomisation, until first discharge) in ICU, hospitalisation after randomisation (until first discharge to rehabilitation, transitional care, long-term care or home): descriptive statistics, Kaplan-Meier estimates, censored after drop-out and death.
- Ventilation-free days, vasopressor-free days until (first) discharge of ICU or maximum 28 days: descriptive statistics

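### SOFA scoring has no rule for renal replacement therapy or for non-catecholamine vasopressors, so more organ support can lower the score or leave it undefined

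*Protocol*

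**What the plan says.** **Kidney.** Protocol 14.1 says: "Serum creatinine and urinary output determine this sub-score. The worst value is part of the CRF variables". The table gives 0 to 4 points by creatinine, with two urine criteria: below 500 ml/24h scores at least 3, and 4 points apply at a creatinine of 5.0 mg/dl or more "or urinary output <200 ml/24h". RRT does not appear.

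**Circulation.** The same appendix says: "Mean arterial pressure (MAP) and the need for catecholamine determine the assigned points". Row 0 reads "MAP ≥ 70 and no vasopressors", and row 1 has the same vasopressor condition with a lower MAP. Rows 2 to 4 list only dopamine, dobutamine and adrenaline or noradrenaline.

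**Data collected.** Protocol 7.5 requires, for each ICU day, "Recording of intensive care interventions (ITN, CIC, AC, RRT, mechanical ventilation, ECMO, haemodynamic monitoring) on the respective trial day" and "Recording of concomitant medication with catecholamines and inotropes, diuretics, fluid therapy". Protocol 6.7 says: "There are no restrictions to concomitant medication and therapies during the trial".

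**Use of the score.** Protocol 11.3.2 has "Organ failure defined as increase in the daily recorded SOFA (day 1 to 28) from a value <2 to a value ≥ 2" and counts such failures per patient. SAP 6.7 uses different cuts: dysfunction is any subscore above 2, and failure is any subscore above 3. The SAP's only SOFA data rules are carrying forward short gaps in GCS (5.1) and the comparison with baseline (5.3).

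**The concern.** SOFA and organ failure are meant to show whether albumin changes organ function. RRT clears creatinine, so a rule based on creatinine and urine alone can read the treatment as improvement of the organ. The protocol already guards against this kind of distortion for the brain: Protocol 14.1 scores a sedated patient's GCS as if unsedated. The kidney has no equivalent.

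The cardiovascular table has a related gap. It excludes every vasopressor from the low rows but admits only catecholamines to the high rows.

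The trial is open-label and co-treatment is unrestricted. Protocol 6.5 and 8.2 name hypervolaemia and pulmonary oedema as possible effects of the trial drug, so unequal RRT use between arms is conceivable. If it occurred, the arm with more organ support could show the better SOFA score.

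**Working it through.** The plan states no figure on this point, so there is none to reproduce. The check applies the Protocol 14.1 tables as printed to illustrative patient-days. The creatinine, urine and noradrenaline values are assumptions chosen to fall in different rows.

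**1. Renal subscore when RRT clears creatinine**

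Subscore = the higher of the creatinine points and the urine points.

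| Urine (ml/24h) | Creatinine before → on RRT (mg/dl) | Score before | Score on RRT | Fall |
|---|---|---|---|---|
| 800 | 5.5 → 2.5 | 4 | 2 | 2 |
| 800 | 5.5 → 1.8 | 4 | 1 | 3 |
| 800 | 5.5 → 1.0 | 4 | 0 | 4 |
| 350 | 5.5 → 1.5 | 4 | 3 | 1 |
| 350 | 3.0 → 1.5 | 3 | 3 | 0 |
| 100 | 5.5 → 1.0 | 4 | 4 | 0 |

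The large falls are confined to urine of 500 ml/24h or more.

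**2. Effect on the two organ-failure definitions**

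- *Protocol 11.3.2 (from below 2 to 2 or more, read here as applying to a subscore).* A non-oliguric patient on RRT with creatinine 1.6 scores 1. RRT pauses, creatinine reaches 2.2, and the score is 2. This counts as a new organ failure, although kidney function may not have changed.
- *SAP 6.7 (above 3).* The rebound to 2 does not count. The error here is the reverse. A non-oliguric patient who starts RRT before creatinine reaches 5.0 mg/dl scores at most 3, so the kidney never registers as failed despite dialysis. At 200-499 ml/24h the urine criterion gives 3, which is also not above the cut.

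**3. Cardiovascular subscore**

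- Noradrenaline 0.15 µg/kg/min scores 4. If a non-catecholamine agent is added and noradrenaline falls to 0.08, the score is 3, which is below the SAP failure cut.
- On a non-catecholamine agent alone, rows 0 and 1 fail because a vasopressor is running, and rows 2 to 4 fail because no listed drug is running. The score is undefined.

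**4. What a difference between arms would do**

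Shift in mean SOFA per ICU day = difference between arms in the share of ICU days on RRT × share of RRT days that are non-oliguric with cleared creatinine × points lost.

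Assume a non-oliguric share of 0.20-0.40 and 3 points lost (4 to 1):

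- difference of 5 percentage points: 0.05 × 0.20 × 3 = 0.03 to 0.05 × 0.40 × 3 = 0.06
- difference of 10 percentage points: 0.10 × 0.20 × 3 = 0.06 to 0.10 × 0.40 × 3 = 0.12

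None of these inputs is in the documents. The range only shows the order of magnitude under the stated assumptions.

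**The case against.** Several counter-arguments stand.

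- **The same rule applies in both arms.** A reader might multiply an assumed 30-50% of ICU days on RRT by 20-40% non-oliguric and by 3 points (0.30 × 0.20 × 3 = 0.18; 0.50 × 0.40 × 3 = 0.60) and call the result the bias. It is an assumed understatement common to both arms; only a difference in use produces bias. Protocol 8.2 says about half the patients have acute kidney failure, which is not a rate of RRT.
- **Worst daily values are used.** A high creatinine before a session on the same day still counts, which delays the fall.
- **Patient-level counts are buffered.** Under the SAP's any-subscore rule, a patient whose other subscore exceeds 3 is counted anyway. If the count is over the whole stay, a renal score of 4 before RRT also remains counted.
- **RRT is visible elsewhere.** SAP 6.2 and 6.8.3 tabulate it by treatment group, and SAP 6.8.1 reports renal events as a category. A difference in use could be seen, though SOFA would not be adjusted for it.
- **An RRT-adjusted score has its own weakness.** A patient dialysed for fluid overload with creatinine 1.0 mg/dl and good urine output would move from 0 to 4 because of an unblinded decision. This argues for a sensitivity analysis and against replacing the main score.

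Three stronger readings are tempting but not supported. First, the table does not give a better score to a day on a non-catecholamine agent alone; it gives none. Second, a reader might infer that these agents go unrecorded, or that such days are counted as vasopressor-free. Protocol 6.7 also requires concomitant medication to be documented, the eCRF is not among the documents, and neither document says which drugs define vasopressor-free days. Third, neither document has a recovery endpoint.

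**Conclusion.** The point holds in limited form. The renal rule as written can record increased organ support as a fall of 3 to 4 points when urine is at least 500 ml/24h. The fall is at most 1 point at 200-499 ml/24h and nil below 200 ml/24h. It can create a new failure under Protocol 11.3.2 and miss a dialysed patient's renal failure under SAP 6.7. The cardiovascular table leaves one kind of day without a score and allows a one-point fall when an added agent spares noradrenaline.

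Bias between arms requires different use of RRT or of these vasopressors, and the documents give no basis for estimating its size. The stakes are modest: SOFA and organ failure are secondary endpoints, described and compared exploratively, and the primary analysis of 90-day mortality is unaffected. The point is worth correcting because the remedy is cheap and a scoring rule chosen after results by arm are known would be less credible.

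**What to change.** In the SAP, before any comparison by arm:

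1. Pre-specify an additional SOFA and organ-failure analysis that sets the renal subscore to 4 on every day with recorded RRT and over a gap between sessions whose length is fixed in advance. Show it beside the unmodified score, which stays the main one.
2. State how a day on a non-catecholamine vasopressor, alone or added to a catecholamine, is scored in the cardiovascular subscore.
3. State that such a day is not vasopressor-free.
4. Confirm that the daily eCRF captures these agents. If it does not, add one item, filled from the chart.

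The cost is a few lines of SAP text, one extra analysis from RRT data already collected and possibly one eCRF item. Patient care does not change. The small downside is that the adjusted score depends on an unblinded treatment decision, which the report should say.
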